9.5.5.4. Follow-up Visit (D52)

During this visit, which will occur 45 days after the second treatment session, no treatment will be performed.

The investigators will:

- Collect the **SCAT5 symptom evaluation tool form** that was completed by the patient at D14
- **Collect any AEs** that occurred since the last visit
- **Check** that, between the first and second treatment sessions, patients did not have a **second concussion**. If that's the case, remaining performance evaluations won't be performed.
- If applicable, **perform the following tests**:
 - NPC
 - Cover test
 - Maddox rod test
 - Static stabilometric test

The patient will be asked to evaluate the intensity of his/her symptoms using the SCAT5 symptom evaluation tool.

Finally, a **blood sample** will be obtained by the nurse.

Once all these evaluations have been conducted and all the required data have been collected, a treatment session may be offered to patients who did not become **contraindicated** to RGn550 treatment after the second treatment session.

Patients who became contraindicated to RGn550 treatment or had a second concussion between the first and second treatment session will not come on site for this visit since no further performance evaluations will be performed for these patients. However, the principal investigator will call them on D52 to collect any AEs that occurred since the last visit.

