9.5.5.2. Second Treatment Session Visit (D7)

This visit will occur at D7 and will correspond to the second treatment session.

Before treatment, the investigators will **collect any AEs** that occurred since the last visit.

Following that, they will **check** that:

- Patients did not have a **second concussion** between the first and second treatment sessions, as this could impact the performance evaluations
- Patients did not become **contraindicated** to RGn550 treatment between the first and second treatment sessions

If that's the case, the second treatment session will not be performed nor any of the remaining performance evaluations described below.

If applicable, before treatment:

- The investigators will **perform the following tests** following the methodology described above:
 - NPC
 - Cover test
 - Maddox rod test
 - Static stabilometric test
- The patient will be asked to evaluate the intensity of his/her symptoms using the SCAT5 symptom evaluation tool.

The patients will then be **treated** for 20 min, as per their assigned group and using the same RGn550 device that was used at D0.

Following treatment, the investigators will:

- **Perform the following tests:**
 - NPC
 - Cover test
 - Maddox rod test
 - Static stabilometric test
 - TMT A&B
- **Collect any AEs and DDs** that occurred during the visit.
- Give the patient a **SCAT5 symptom evaluation tool form** for remote completion by the patient at D14.

| | | |
|--------|---|---|
| RGnCON | Clinical Investigation Plan Version 2.0 - 11 August 2022 |  |
|--------|---|---|

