9.13.3. Safety Reporting to Sponsor

Per Article 80 of the European Regulation 2017/745, the following events shall be recorded:

- Any AE of a type identified in the CIP as being critical to the evaluation of the results of that clinical investigation
- Any SAEs
- Any DD that might have led to a SAE if appropriate action had not been taken intervention had not occurred, or circumstances had been less fortunate
- Any new findings in relation to the above events.

The following events that occur in patients included in RGnCON from inclusion to the end of the 52-day follow-up period will thus be recorded:

- All AEs, including SAEs
- All DDs
- Any new findings in relation to AEs and DDs.

AEs will be reported using the Adverse Event form of the eCRF while DDs will be reported using the Device Deficiency form. The date of the event, its severity, causality, treatment and resolution will notably be collected.

These events will be reported immediately to REGEnLIFE and no later than 3 calendar days after the investigator becomes aware of the event.

If needed, the investigations site team or [REDACTED] can contact REGEnLIFE's materiovigilance department via email ([contact]) or phone ([contact]).

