## 8.5. Efficacy analysis

### 8.5.1. Analysis of the secondary performance endpoints

The secondary performance endpoints will be analyzed in the FAS population by treatment groups, excluding data that would be collected after the following intercurrent event: treatment group switch during follow-up.

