### 8.5.1.5. Sensitivity analysis

A sensitivity analysis will be conducted on the secondary performance endpoints (oculomotor and oculopostural functions, balance function, executive function (TMT A&B) , concussion syndrome symptoms (SCAT5) and blood markers) in the FAS without excluding any data that would be collected after intercurrent events.

Of note, data of patients with a second concussion that occurred after RGn550 first treatment session will be considered before the onset of the concussion. Similarly, data of patients with a contraindication to RGn550 that occurred after RGn550 first treatment session will be considered before the onset of the contraindication.

This sensitivity analysis will be performed only if the proportion of excluded patients exceeds 10% (at least 5 patients excluded).

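### The D52 second-concussion check repeats the D0–D7 interval, and the plan does not say clearly whether data after a later re-injury leave the main performance analysis

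*Protocol*

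**What the plan says.** **Visits.** At D7, Protocol 9.5.5.2 has investigators check for a second concussion "between the first and second treatment sessions, as this could impact the performance evaluations". A patient who had one gets no second session and none of the remaining performance evaluations. At D52, Protocol 9.5.5.4 asks them to check that, "between the first and second treatment sessions, patients did not have a" second concussion, and adds: "If that's the case, remaining performance evaluations won't be performed". The same section says that patients who "had a second concussion between the first and second treatment session will not come on site for this visit"; they are telephoned for adverse events instead. The D14 contact (9.5.5.3) is a reminder call about the SCAT5 form and contains no re-injury question.

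**Adverse events.** The D52 visit also collects any AEs "that occurred since the last visit". Protocol 9.13.3 states that all AEs "from inclusion to the end of the 52-day follow-up period will thus be recorded", with the date of the event.

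**Analysis.** Protocol 9.6.3.2 and SAP 8.5.1 analyse the performance endpoints in the FAS, "excluding data that would be collected after the following intercurrent event: treatment group switch during follow-up". Both documents then describe a sensitivity analysis that keeps all data collected after intercurrent events. Under that same heading they add that "data of patients with a second concussion that occurred after RGn550 first treatment session will be considered before the onset of the concussion", with a parallel sentence for contraindications. The sensitivity analysis runs only if more than 10% of patients (at least 5) were excluded.

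**The concern.** The protocol's reason for the check is that a second concussion could affect the performance evaluations. That reason holds at least as strongly for D52, which follows 45 days in which athletes may return to sport. Yet the D52 check looks back to the week already covered at D7, and both the stop rule and the no-visit rule are tied to that week. A patient re-injured on, say, day 40 would be tested at D52 under the protocol as written.

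If the analysis then keeps those results, the D52 values for convergence, ocular deviation, balance, SCAT5 and blood markers mix recovery from the index injury with the effect of a new one. A re-injury between D7 and D14 would do the same to the D14 SCAT5 score. The comparison most exposed is the additional model in the SAP note that follows 8.5.1.3. It pools all patients, has a period effect only, and estimates the D0-to-D52 change with no comparator.

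**Working it through.** **1. Intervals side by side.**

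| Text | Second concussion covered |
|---|---|
| Protocol 9.5.5.2, D7 check | D0 to D7 |
| Protocol 9.5.5.4, D52 check | D0 to D7 |
| Protocol 9.5.5.4, no-visit sentence | D0 to D7 |
| Protocol 9.6.3.2 and SAP 8.5.1.5, truncation note | any time after the first session |
| Protocol 9.5.5.4 and 9.13.3, AE collection | up to D52, all AEs |

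Follow-up is 7 + 45 = 52 days. The dedicated check covers 7/52 = 13.5% of it and leaves 45/52 = 86.5% to AE reporting. The truncation note is wider than the visit checks, so the two do not match.

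**2. Which analysis the truncation note governs.** Read literally, the main analysis excludes only data after a group switch, and the note belongs to the sensitivity analysis. But a rule that cuts data fits badly inside an analysis defined as excluding nothing. Read generously, the note is a general data-handling rule placed under the wrong heading. The synopsis does not help: it repeats the main and sensitivity rules without mentioning a second concussion.

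**3. Expected number of cases.** The plan gives no repeat-concussion rate. Its one design figure reproduces (1 − 0.96^50 = 0.8701, stated as 0.87) but plays no part here.

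Inputs: 50 patients; 45/7 = 6.43 weeks; 0.6 to 0.8 concussions per 1,000 athlete-game-hours (Protocol 9.2.1.1.6); assumed 1.33 to 2.67 game-hours per week.

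- Low: 50 × 6.43 × 1.33 × 0.0006 = 0.26 cases.
- High: 50 × 6.43 × 2.67 × 0.0008 = 0.69 cases.
- Chance of at least one (Poisson): 1 − exp(−0.26) = 23% to 1 − exp(−0.69) = 50%.

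Other assumptions:

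- 4 to 12 game-hours per patient over the whole window, with per-patient risk 1 − exp(−rate × hours): 0.12 to 0.48 cases, and an 11% to 38% chance of at least one.
- A 52-day re-injury risk of 2% to 10% at constant hazard: 50 × 0.02 × 45/52 = 0.9 to 50 × 0.10 × 45/52 = 4.3 cases, and a 58% to 99% chance of at least one. At 2% to 6%, the chance of five or more is 0.2% to 12%.

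**4. Effect on a mean.** Assume that one re-injured patient scores 30 SCAT5 points higher at D52. An arm mean of 25 moves by 30/25 = 1.2 points, and the pooled mean of 50 by 30/50 = 0.6 points, on a 132-point scale. Weighted by the 0.26 to 0.69 expected cases, the pooled shift is 0.26 × 0.6 = 0.16 to 0.69 × 0.6 = 0.41 points.

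**The case against.** The strongest reply is that the plan is better protected than the D52 sentence suggests, and much of it stands.

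- A reader might infer that re-injury after D7 goes unscreened. The documents do not support that: AE collection covers the whole window, and a new concussion meets the protocol's AE definition (9.13.1.1). The onset date needed to cut the data should therefore exist. What is missing is any link from that AE to the D52 tests or to the main analysis.
- A reader might infer that the D52 check can never find anyone. It could still find a D0–D7 concussion that was not recognised or disclosed at D7, so the interval should be widened rather than moved.
- Whether data after re-injury are kept or cut is a choice of estimand, and either can be defended. That is fair, but the plan has to make the choice, and its own truncation note indicates which one it intended.
- The case counts assume match play from D7 onwards for everyone, whereas Protocol 9.2.1.1.5 describes a gradual return to activity. This pulls the estimate down, and the 4-to-12-hour range shows by how much.

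**Conclusion.** The inconsistency is real and minor to moderate. The D52 check, its stop rule and the no-visit sentence cover only D0–D7, against the protocol's own reason for checking and its own wider truncation note. The main-analysis text leaves the handling of D14 and D52 data after re-injury unsettled.

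Two stronger conclusions should not be drawn. First, that contaminated D52 data certainly enter the main analysis: this follows only from the literal reading, and the note can also be read as a general rule. Second, that the 5 Hz versus 10 Hz comparison is biased: with 1:1 randomisation nothing suggests that re-injury differs by frequency. The directional exposure lies in within-group and pooled change from D0.

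The primary ADE endpoint is unaffected. The likely number of cases is below one on the protocol's incidence and the assumed game-hours. It rises above one only with an assumed 52-day re-injury risk of a few per cent, for which the documents offer no figure.

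**What to change.** 1. **Protocol 9.5.5.4.** Widen the D52 check to any second concussion since the first treatment session, which matches the truncation note. Reconcile the no-visit sentence with it, so that the text says what is done at D52 for a patient re-injured after D7.
2. **SAP 8.5.1** (and Protocol 9.6.3.2, if amended). State that the existing truncation rule, for second concussion and for contraindication, applies to the main performance analysis. This should include the D14 SCAT5 score and the pooled D0-to-D52 model, with the recorded AE onset date as the cut.
3. **SAP 8.5.1.5.** Remove the truncation rule from the no-exclusion sensitivity analysis. That analysis would then use whatever post-event data were actually collected. Few D52 results may be available, because the stop rule withholds those tests.

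The cost is a phrase and a sentence or two, with no new procedure. SAP version 2.0 followed a data review in July 2023, so the visits may already be complete. The protocol change would then come too late to alter collection, but the SAP change would still work from the AE dates. The truncation rule already stands in the August 2022 protocol, so clarifying its scope would not introduce a new rule after data review. The AE listing would show whether any patient is affected.

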9.4.1. Primary Objective

The primary objective of this investigation is to evaluate the **incidence of RGn550's ADEs** in acute concussion syndrome, when used to deliver, either at a frequency of 5 or 10 Hz, two 20-min treatment sessions at 1 week apart.

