9.5. Clinical Investigation Design

9.5.1. Investigational Medical Devices

Two RGn550 devices producing a 5 Hz frequency and two producing a 10 Hz frequency will be provided by REGEnLIFE to the investigational site. Provided devices will be tracked, during and after the investigation, with assigned serial numbers.

The principal investigator will be trained in the use of RGn550 by REGEnLIFE before the inclusion of the first patient.

Each patient will be treated with the same device throughout the investigation. For a given patient, the other device of the same type (5 Hz or 10 Hz) may only be used in case of malfunction of the initial device.

To maintain simple blinding, the devices will be visually identified as follows:

- The RGn550 devices producing a 5 Hz frequency will be labeled as: Device A1 and Device A2
- The RGn550 device producing a 10 Hz frequency will be labeled as: Device B1 and Device B2.

To track the use of the devices, the principal investigator will mention in the electronic Case Report Form (eCRF) which RGn550 device was used at each treatment session of each patient. In parallel, he will fulfil a treatment sheet associated with the device in question and write down the number of the treated patient, date of treatment, number of treatment session and duration of treatment.

The maximal overall exposure of patients to RGn550 will be of 1 week, since the second, and last, treatment session is planned at Day 7. Exposure during a treatment session will be of 20 min.

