9.5.3.5. End of Investigation

The end of the investigation is defined as the completion of the last patient last visit. The last patient last visit will occur when the last patient either completes the 52-day follow-up visit or prematurely terminate the investigation.

A patient may prematurely terminate the investigation for the following reasons:

- Screen failure

| | | |
|--------|---|---|
| RGnCON | Clinical Investigation Plan Version 2.0 - 11 August 2022 |  |
|--------|---|---|

- Withdrawal
- Lost to follow-up
- Death.

For each patient, an end-of-investigation form will be filled in within the eCRF by the investigator, whether or not they have completed the investigation. In case of premature termination, the date and reason will be collected.

Screen failure

A screen failure occurs when a patient was included while he/she has one or several non-inclusion criteria and/or does not have one or several inclusion criteria.

In that case, the investigators must ensure that the reason for screen failure is adequately documented in the patient's medical file and the eCRF.

Withdrawal

Patients may voluntarily withdraw from the investigation at any time. A patient may also be withdrawn from the investigation at the investigators' discretion.

In case of withdrawal, the investigators must ensure that the date and reason for the withdrawal is adequately documented in the patient's medical file and the eCRF.

Data from all patients who left the investigation prematurely will be analyzed until the date of withdrawal.

Lost to Follow-Up

When investigators do not have any news from a patient, they will make at least three attempts to contact the patient as well as the patient's general practitioner and/or a family member if known. If all these attempts fail, the investigators can then declare the patient as "lost to follow-up". In that case, every effort will be made to obtain necessary information to complete the eCRF.

Each attempt should be documented in the patient's medical file with the date, description of the three unsuccessful contacts along with the contact method (e.g., telephone, letter with acknowledgement of receipt).

Of note, to prevent lost-of follow-up patients, automatic alerts will be sent via emails to the site to remind them of upcoming visits with their patients.

Data from patients who were lost to follow-up will be analyzed until the date of loss to follow-up.

Death

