#### Notes / definitions:

- AEs will be coded using the MedDRA dictionary version 25.0.
- Adverse Device Effects (ADE) are defined as all AEs recorded in the eCRF with a possible, probable or causal relationship to RGn550.
- ADE occurring during the first session (at D0) are defined as all ADE with a start date equal to the date of D0.
- ADE occurring during the second session (at D7) are defined as all ADE with a start date equal to the date of D7.

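### The protocol allows an optional RGn550 session at D52, which contradicts the stated two-session, one-week maximum exposure, and schedules no AE or DD collection after it.

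*Protocol*

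**What the plan says.** Protocol 9.5.5.4 opens its description of the D52 visit with "During this visit, which will occur 45 days after the second treatment session, no treatment will be performed". Later in the same section it says "Once all these evaluations have been conducted and all the required data have been collected, a treatment session may be offered to patients", provided that they have not become contraindicated since the second session.

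Other parts of the protocol describe two sessions only:

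- Section 9.5.1: "The maximal overall exposure of patients to RGn550 will be of 1 week, since the second, and last, treatment session is planned at Day 7".
- Section 9.4.1 sets the primary objective for the device "when used to deliver, either at a frequency of 5 or 10 Hz, two 20-min treatment sessions at 1 week apart".
- Table 2 in 9.5.5.5 marks the treatment session at D0 and D7 and leaves D52 blank.

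On safety recording, 9.13.3 states that AEs and DDs "from inclusion to the end of the 52-day follow-up period will thus be recorded". Section 9.5.3.5 says: "The last patient last visit will occur when the last patient either completes the 52-day follow-up visit or prematurely terminate the investigation".

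In the SAP, the notes under 6.2.1 state: "Adverse Device Effects (ADE) are defined as all AEs recorded in the eCRF with a possible, probable or causal relationship to RGn550". The same notes define ADEs by session for D0 and D7 only.

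**The concern.** Two things are wrong. First, the stated maximum exposure is false for every patient who accepts the D52 offer, and 9.5.5.4 contradicts itself. Second, the offer comes after the D52 data collection is finished, so the safety step precedes the exposure that it would need to cover.

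This matters because safety is the primary purpose of the trial. The device is not CE-marked (9.1.1), 9.2.3 describes the trial as the first evaluation of its safety in this population, and there is no Data Safety Monitoring Board (9.13.6). Using the device under the plan without scheduled follow-up leaves those patients unobserved.

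There is also a smaller analysis problem. The primary objective concerns two sessions, but the primary endpoint in 9.5.4.1 covers ADEs throughout the investigation. The SAP has no rule for an ADE that follows a third session.

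**Working it through.** **1. Collection after each session**

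| Session | AE/DD collection after treatment | Source |
|---|---|---|
| D0 | Yes, during the visit | Protocol 9.5.5.1, Table 2 |
| D7 | Yes, during the visit | Protocol 9.5.5.2, Table 2 |
| D52 (optional) | None | Protocol 9.5.5.4, Table 2 |

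The D52 AE step covers events since the previous visit. The AE/DD row of Table 2 refers to events that have already occurred, and its D52 column is not split into before and after treatment. No later visit or call exists. An event on D52 itself can still be recorded under 9.13.3; an event starting afterwards falls outside the window.

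**2. Exposure**

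- As stated: 2 sessions × 20 min = 40 min over 7 days.
- With the D52 session: 3 × 20 = 60 min over 52 days, an increase of 60/40 − 1 = 50%.
- If all 50 patients have both planned sessions and all accept, 50 of 150 sessions are at D52.

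**3. The plan's own figure**

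Protocol 9.6.1 gives a probability of 0.87 of at least one ADE with N = 50 and an ADE probability of 0.04. Check: 1 − 0.96^50 = 0.8701, which agrees. The point made here does not depend on it.

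**4. Chance of an ADE in the D52 sessions**

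The documents give neither uptake nor a per-session rate. Assume that 0.04 is the risk over both planned sessions, with equal and independent risk per session, and that a D52 session carries the same risk:

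p = 1 − (1 − 0.04)^0.5 = 0.0202 per session.

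For n acceptors:

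- the chance of at least one D52-session ADE is 1 − (1 − p)^n;
- the D52 share of sessions is n/(100 + n);
- the expected number of patients newly counted in the primary endpoint is at most n × 0.96 × 0.0202, because only a patient without an earlier ADE adds to the count. It is an upper limit because it treats every event as same-day and recorded.

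| Acceptors n | P(at least one ADE) | Share of sessions | Expected patients added (at most) | Shift on N = 50 |
|---|---|---|---|---|
| 5 | 0.097 | 4.8% | 0.10 | 0.2 points |
| 12 | 0.217 | 10.7% | 0.23 | 0.5 points |
| 25 | 0.400 | 20.0% | 0.48 | 1.0 points |
| 50 | 0.640 | 33.3% | 0.97 | 1.9 points |

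**5. Effect of one counted event on the primary estimate**

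The expected count without the D52 session is 50 × 0.04 = 2. Exact Clopper-Pearson 95% intervals:

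- 2/50 = 4.0% (0.5 to 13.7)
- 3/50 = 6.0% (1.3 to 16.5)

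One added patient is a chosen scenario. It is close to the expectation only if all 50 patients accept.

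**The case against.** The strongest counter-argument is that the gap is narrow. The principal investigator applies the treatment on site (9.5.5), must record all AEs and DDs to the end of the 52-day follow-up, and must report them within 3 calendar days of becoming aware (9.13.3). The sponsor's duty to report device-related serious events to the authority (9.13.4) has no D52 cut-off. The anticipated-ADE lists are redacted, so the timing of likely events cannot be judged, and 9.3.2 expects no severe ADEs. The effect on the primary proportion is small beside an interval about 13 points wide. It could be isolated afterwards, since event dates and the device used at each session are recorded. Performance endpoints are untouched, because all measurements precede the offer.

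Much of this stands. Same-day events are recordable, performance data are safe, and the shift in the primary proportion is modest. Leaving D52-session ADEs out does not bias the two-session estimate. But a duty to report an event once known does not schedule anyone to look for it, and 9.13.4 concerns serious events and qualifying DDs only. Logging the device and excluding contraindicated patients do not provide follow-up either. None of these points reconciles 9.5.5.4 with 9.5.1.

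**Conclusion.** The concern holds and should be fixed. Two parts follow from the text alone, without any assumption: the D52 offer contradicts the exposure limit, the two-session objective, the schedule and the opening of its own section; and no AE or DD collection is scheduled after it.

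The size of the consequence does rest on assumptions. With 0.0202 risk per session and 5 to 50 acceptors, the chance of at least one ADE in the D52 sessions runs from about 0.10 to 0.64. The expected effect on the primary proportion is at most about 0.2 to 1.9 percentage points. The weight of the point therefore lies in safety follow-up and the accuracy of the exposure statement; mixing a third exposure into the primary estimate is secondary.

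**What to change.** Either delete the offer from 9.5.5.4, or keep it and make three changes:

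1. Correct the exposure statement in 9.5.1, the opening sentence of 9.5.5.4 and the treatment row of Table 2.
2. Add AE and DD collection after the session, and extend the 9.13.3 window briefly, for example to one follow-up call.
3. State in SAP 6.1 and 8.4 that ADEs with onset after a D52 session are tabulated separately from the two-session primary endpoint.

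Keeping the offer costs a protocol amendment, one more eCRF entry or call per acceptor, and one more safety listing. Deleting it costs only the amendment, but patients lose the optional session. If all visits are already complete (Protocol 9.17 planned the last one for February 2023), the SAP rule and a separate listing of any D52 sessions and their recorded ADEs remain feasible.
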